20.6 Appendix 6: Common Terminology Criteria for Adverse Events v. 5.0

The CTCAE (version 5) for download can be found at:

http:\\ctep.cancer.gov/protocolDevelopment/electronic_applications/docs/CTCAE_v5_Quick_Reference_5x7.pdf

Examples for grading of terms are shown below in Figure 4 Example of Grading for General Disorders and Administration Site Conditions and Figure 5 Example of Grading for Laboratory Abnormalities (Investigations).

Hypothermia - Definition: A disorder characterize	Grade 1	35 - >32 degrees C; 95 - >89.6 degrees F	32 - >28 degrees C; 89.6 - >82.4 degrees F	<=28 degrees C; 82.4 degrees	Grade 5
	d by an abnormally low body	temperature. Treatment is requir	ed when the body temperature is	F; life-threatening consequences (e.g., coma, hypotension, pulmonary edema, acidemia, ventricular fibrillation) s 3SC (95F) or below.	
Navigational Note: - Infusion site extravasation Page 1	ainless edema	Erythema with associated symptoms (e.g., edema, pain, induration, phlebitis)	Ulceration or necrosis; severe tissue damage; operative intervention indicated	Life-threatening consequences; urgent intervention indicated	Death
Definition: A disorder characterize and marked discomfort at the infu Navigational Note: -	Control of the Contro				l g sensation
Injection site reaction Te	enderness with or without ssociated symptoms (e.g., armth, erythema, itching)	Pain; lipodystrophy; edema; phlebitis	Ulceration or necrosis; severe tissue damage; operative intervention indicated	Life-threatening consequences; urgent intervention indicated	Death
Definition: A disorder characterize Navigational Note: -	d by an intense adverse reacti	ion (usually immunologic) develo	ping at the site of an injection.		
Localized edema Lo	ocalized to dependent areas, o disability or functional opairment	Moderate localized edema and intervention indicated; limiting instrumental ADL	Severe localized edema and intervention indicated; limiting self care ADL	100	58
Definition: A disorder characterize Navigational Note: Prior to using t Edema neck; Nervous system disor edema or Pulmonary edema: Skin a	his term consider specific ede ders: Edema cerebral; Reprod	ma areas: General disorders and luctive system and breast disorde	administration site conditions: Ed rs: Genital edema; Respiratory, t		
Malaise U	neasiness or lack of well eing	Uneasiness or lack of well being limiting instrumental ADL	Uneasiness or lack of well being limiting self-care ADL	7-50	9
Definition: A disorder characterize Navigational Note: -	d by a feeling of general disco	mfort or uneasiness, an out-of-so	orts feeling.	,	
Multi-organ failure -		a *	Shock with azotemia and acid-base disturbances; significant coagulation abnormalities	Life-threatening consequences (e.g., vasopressor dependent and oliguric or anuric or ischemic colitis or lactic acidosis)	Death

CTCAE v5.0 - November 27, 2017 Back to TOC Page 42

Figure 4 Example of Grading for General Disorders and Administration Site Conditions

20.6 Appendix 6: Common Terminology Criteria for Adverse Events v. 5.0 cont.

		Investigations			10
CTCAE Term	Grade 1	Grade 2	Grade 3	Grade 4	Grade
Lipase increased	>ULN - 1.5 x ULN	>1.5 - 2.0 x ULN; >2.0 - 5.0 x ULN and asymptomatic	>2.0 - 5.0 x ULN with signs or symptoms; >5.0 x ULN and asymptomatic	>5.0 x ULN and with signs or symptoms	5) S)
	laboratory test results that indica	te an increase in the level of lipa s	e in a biological specimen.		
Navigational Note: -	co.		76	9	
Lymphocyte count decreased	<lln -="" 0.8="" 800="" <lln="" mm3;="" x
10e9/L</lln>	<800 - 500/mm3; <0.8 - 0.5 x 10e9 /L	<500 - 200/mm3; <0.5 - 0.2 x 10e9 /L	<200/mm3; <0.2 x 10e9 /L	2
Definition: A finding based on Navigational Note: -	laboratory test results that indica	te a decrease in number of lymph	ocytes in a blood specimen.		
Lymphocyte count increased		>4000/mm3 - 20,000/mm3	>20,000/mm3		3
Definition: A finding based on Navigational Note: -	laboratory test results that indica	te an abnormal increase in the nu	imber of lymphocytes in the bloo	d, effusions or bone marrow.	
Neutrophil count decreased	<lln -="" 1.5<br="" 1500="" <lln="" mm3;="">x 10e9 /L</lln>	<1500 - 1000/mm3; <1.5 - 1.0 x 10e9 /L	<1000 - 500/mm3; <1.0 - 0.5 x 10e9 /L	<500/mm3; <0.5 x 10e9 /L	2
Definition: A finding based on Navigational Note: -	laboratory test results that indica	te a decrease in number of neutr	ophils in a blood specimen.		18 18
Pancreatic enzymes decreased	<lln and="" asymptomatic<="" td="">Increase in stool frequency, bulk, or odor; steatorrhea	Sequelae of absorption deficiency	HET:	8	</lln>	Increase in stool frequency, bulk, or odor; steatorrhea	Sequelae of absorption deficiency	HET:	8
Definition: A finding based on Navigational Note: -	laboratory test results that indica	te an decrease in levels of pancre	atic enzymes in a biological speci	men.	33
Platelet count decreased	<lln -="" -<br="" 75,000="" <lln="" mm3;="">75.0 x 10e9 /L</lln>	<75,000 - 50,000/mm3; <75.0 - 50.0 x 10e9 /L	<50,000 - 25,000/mm3; <50.0 - 25.0 x 10e9 /L	<25,000/mm3; <25.0 x 10e9	-
Definition: A finding based on Navigational Note: -	laboratory test results that indica			1.7-	(d)
Serum amylase increased	>ULN - 1.5 x ULN	>1.5 - 2.0 x ULN; >2.0 - 5.0 x ULN and asymptomatic	>2.0 - 5.0 x ULN with signs or symptoms; >5.0 x ULN and asymptomatic	>5.0 x ULN and with signs or symptoms	
Definition: A finding based on Navigational Note: -	laboratory test results that indica	te an increase in the levels of am	ylase in a serum specimen.		25 00
Thyroid stimulating hormone increased	TSH increased and no intervention initiated	≅ "		SEC.	2
	rized by an increase in thyroid sti ion initiated or symptomatic, rep		hyroidism.		10

CTCAE v5.0 – November 27, 2017 Back to TOC Page 82

Figure 5 Example of Grading for Laboratory Abnormalities (Investigations)

20.7 Appendix 7: Sampson's Criteria of Anaphylaxis

ANAPHYLAXIS: Sampson's definition of anaphylaxis (clinical definition) is the acute onset of illness (minutes to several hours) which involves **SKIN**, **MUCOSAL TISSUE**, **or BOTH** (e.g., generalized hives, pruritus or flushing, swollen lips-tongue uvula) **with 1 OR more of the following** (Sampson, 2006):

- **RESPIRATORY**: Airway compromise (e.g., dyspnea, wheeze, or bronchospasm, stridor, reduced PEF, hypoxemia)
- **CIRCULATORY**: Reduced blood pressure or associated symptoms of end-organ dysfunction (e.g., hypotonia, syncope)

OR

2 or MORE of the following that occur rapidly after exposure:

- SKIN, MUCOSAL TISSUE: e.g., generalized hives, itch-flush, swollen lips-tongue-uvula
- **RESPIRATORY**: Airway compromise (e.g., dyspnea, wheeze, or bronchospasm, stridor and reduced PEF)
- **CIRCULATORY**: Reduced blood pressure or associated symptoms of end-organ dysfunction (e.g., hypotonia, syncope)
- **GASTROINTESTINAL**: Persistent gastrointestinal symptoms (e.g., crampy abdominal pain, vomiting, nausea, diarrhea)

20.8 Appendix 8: Hepatitis B and Hepatitis C Serologic Testing Details

Hepatitis B Testing Details

HBsAg positive subjects are excluded. However, in case of past infections/vaccinations in order to qualify, the subject's testing status needs to align with the information in Table 8.

Table 8 Hepatitis B Testing

Past Infection	on (Resolved)		Vacci	nated
HBsAg	Negative		HBsAg	Negative
Anti-HBc	Positive	Or	Anti-HBc	Negative
Anti-HBs	Positive		Anti-HBs	Positive

Hepatitis C Testing Details

Anti-HCV positive and HCV-RNA positive are excluded. In order to qualify for enrollment, the subject's testing status needs to align with the information in Table 9.

Table 9 Hepatitis C Testing

Non-R	eactive		Past Infection	on (Resolved)
Anti- HCV	Negative	Or	Anti- HCV	Positive
			HCV RNA	Negative

20.9 Appendix 9: Open Label Extension Period (Optional)

20.9.1 Summary of the Open-Label Extended Dosing Period

Subjects who complete the double-blind, placebo-controlled treatment period (including the Day 85 study visit) and meet the open-label extended dosing eligibility criteria will be given the option to receive 6 doses of 300 mg lirentelimab SC through the open-label extension (OLE) dosing period.

On Day 85 (± 5 days) of the double-blind period, eligible subjects participating in the OLE period will begin following the OLE Schedule of Assessments (Table 10) and will no longer follow the Double-Blind Period Schedule of Assessments (Table 1). The subjects starting the OLE period on Day 85 of the double-blind period do not need to repeat any assessments that overlap with Day 85 from the double-blind period.

The OLE dosing period is summarized as follows:

- The Investigator will evaluate whether the subject is eligible for OLE. If eligible, the subject will be given the option to participate in the OLE period and receive 6 doses of open-label 300 mg lirentelimab SC administered every 2 weeks starting on Day 85 of the double-blind period, which will be considered Day 1 of the OLE period. OLE dosing may be delayed for up to 7 days after completion of the Day 85 visit.
- On Day 85, eligible subjects who choose to participate in the OLE period will begin following the OLE Schedule of Events (Table 10). Subjects starting the OLE period on Day 85 of the double-blind period do not need to repeat any assessments that overlap with Day 85 from the double-blind period.
- Day 1 of the OLE can occur up to 7 days following Day 85 of the double-blind period. In case Day 1 of the OLE is not the same as Day 85 of the double-blind period, applicable subjects (women of childbearing potential) will have to take a urine dipstick pregnancy test.
- Subsequent doses will be given on OLE Days 15, 29, 43, 57, and 71 (\pm 5 days).
- All differential blood counts will be blinded to the Sponsor and the site until after OLE Day 1 dosing.
- Subjects will remain at the site for at least 1 hour of observation after each dose. In the event of an IRR, the subject may require prolonged observation (>1 hour or until the symptoms resolve), as per Investigator discretion.

- Subjects will be followed for approximately 12 weeks after the last dose. Follow-up visits will occur on OLE Days 85, 127, and 155 (14, 56, and 84 [±5] days) after the last dose of open-label study drug.
- If absolute lymphocyte and/or eosinophil counts have not recovered by the OLE Day 155 visit (last follow-up visit), subjects will return approximately every 28 days for extended follow-up until counts have recovered.
- If extended follow-up is required, data collection will be limited to hematology, SAE, and AESI.

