2.3 Overview of Clinical Studies

Lirentelimab IV, administered as a monthly intravenous infusion, has previously been tested in over 700 healthy volunteers and in subjects with indolent systemic mastocytosis (ISM), chronic urticaria (CU), severe allergic conjunctivitis (AC), mast cell gastritis, eosinophilic gastritis (EG) and/or eosinophilic duodenitis (EoD), and eosinophilic esophagitis (EoE). Multiple monthly doses of 3 mg/kg have been given to subjects with ISM, CU, severe AC, EG and/or EoD, and EoE.

In general, lirentelimab IV has been well tolerated. The most common treatment-emergent adverse events (TEAE) observed with IV infusion were mild to moderate infusion-related reactions (IRR). The IRR were mostly mild to moderate, and occurred most often during the first infusion. IRR that were deemed more serious typically resolved within 24 hours, and additional corticosteroids and/or antihistamines were used in cases when slowing the rate of infusion and additional supportive care alone did not resolve the issue. Common symptoms of IRR were headache, nausea, sweating, flushing, and redness. Most IRR that occurred during the infusion could be managed by slowing or temporary interruption of the infusion, with minimal intervention. In subjects with ISM, CU, severe AC, and EG/EoD, fewer adverse events (AE) including IRR were reported during the second and subsequent infusions when compared to the first infusion. The risk of IRR has been substantially reduced by administration of a single dose of oral corticosteroid (e.g., prednisone 60 mg) given orally 12 to 24 hours prior to the first dose of lirentelimab IV.

Study AK002-017 evaluated the PK and PD of lirentelimab IV and SC in healthy volunteers. Subjects received 0.3, 1, 3, or 5 mg/kg or a fixed dose of 300 mg or 450 mg lirentelimab SC, or 1 mg/kg or 3 mg/kg lirentelimab IV. In each of the SC cohorts, 8 subjects were randomized to lirentelimab (6 per group) or placebo (2 per group) in a double-blind manner; 12 subjects received lirentelimab IV (6 subjects per group) in an open-label manner.

The study showed that the PD effect (depletion of blood eosinophils) occurred within 1 hour of dosing and lasted for at least 1 month at IV and SC doses of 1 mg/kg and for 3 months at all higher IV and SC doses. The SC injections were well tolerated, and no injection site reactions or general injection reactions were noted at any dose demonstrating suitability for further evaluation.

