11.3 Blinding

The identity of test and control treatments will not be known to Investigators, Sponsor, research staff, subjects, or the study monitor. The following study procedures will be in place to ensure double-blind administration of study treatments:

- Access to the randomization codes will be strictly controlled by the IRT system.
- Throughout the double-blind study, the blind should remain unbroken except for an emergency when knowledge of the subject's study medication is necessary for further management or if required for regulatory reporting. The Medical Monitor approves any emergency blind break, if at all possible, prior to the unblinding.
- The lirentelimab SC and placebo SC administered by SC injection will be identical in appearance.
- Results from the analysis of blood samples for PK and ADA will not be provided to the Investigator and Sponsor until after final database lock of the double-blind study.
- Results from the analysis of blood samples for histamine/tryptase tests (collected in case of possible anaphylaxis) will not be provided to the Investigator and Sponsor until after final database lock of the double-blind study, unless required for immediate safety reasons.
- Results of the assessments noted below will not be provided to the Investigator and Sponsor until after final database lock of the double-blind study to avoid bias. The results will be reviewed on an ongoing basis by the Safety Monitor and escalated as appropriate.
 - Differential cell counts including neutrophils, eosinophils, basophils, monocytes, and lymphocytes.

Other than under the conditions described above, the study blind will be revealed on completion of the study as noted in Section 17.4.

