12.1.10 Complete Blood Count with Differential

Blood for CBC with differential, including absolute blood eosinophil count, will be obtained at screening, just prior to each SC injection, and 1 hour (±15 minutes) after the end of each SC injection, as well as on all follow-up days 85, 127, and 155 (±5) or 14, 56, and 84 (±5) days after last dose, if ET. The blood sample will be processed and shipped in accordance with the Laboratory Manual and lab kit instructions. A central laboratory will analyze the blood sample and provide results for CBC with differential including hemoglobin, hematocrit, platelet count,

red blood cell count, white blood cell count, and absolute differential count (neutrophils, lymphocytes, monocytes, eosinophils, and basophils).

During the double-blind period, all differential blood counts from Day 1 (post-dose) through the end of the subject's participation will be blinded to the Sponsor and the site. An unscheduled CBC may be collected at the request of the Safety Monitor. The blood differential test results (neutrophils, eosinophils, basophils, monocytes, and lymphocytes) will be blinded from the Investigator and Sponsor from post-dose Day 1 through Day 155 or ET and until database lock has occurred. If a subject continues to the OLE period of the study, all differential blood counts will be blinded for the first (OLE Day 1) predose assessments and will be unblinded after the subject has received the first dose of the study drug.

As described in the Investigator's Brochure, changes in certain lab results are a part of the expected effects of lirentelimab and could potentially introduce bias in blinded members of the study. The Safety Monitor will have real-time access to these laboratory results and will review and escalate any concerns/issues to the Medical Monitor and/or the site as appropriate. An unscheduled CBC with differential may be collected if requested by the Safety Monitor. All panic alerts for blinded values will be sent to the Safety Monitor and evaluated in real time.

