12.3 Clinical Laboratory Measurements

Blood and urine samples for clinical safety laboratory tests will be collected at the time points described below. Investigators may have additional laboratory tests performed for the purpose of planning treatment administration or following AE or abnormal laboratory values.

The site will process and ship blood and urine samples per central laboratory instructions. A central laboratory or designee will analyze blood and urine samples and provide results for the following clinical safety laboratory tests.

Clinical laboratory testing may be performed locally, if necessary, with prior approval from Allakos. The site will strive to use the central laboratory whenever possible.

For any laboratory test value outside the reference range, the Investigator will determine clinical significance: Not Clinically Significant (NCS) or Clinically Significant (CS). An abnormal laboratory value should be deemed CS if any of the following conditions are met:

- The abnormality suggests a disease and/or organ toxicity that is new or has worsened from baseline.
- The abnormality is of a degree that requires additional active management, e.g., change of study drug dose, discontinuation of the study drug, close observation, more frequent follow-up assessments, or further diagnostic investigation.

Therefore, a clinically significant lab value is one that indicates a new disease process, an exacerbation or worsening of an existing condition, or requires further action to be taken. For any laboratory test value outside the reference range that the Investigator considers clinically significant, the Investigator will:

- Repeat the test to verify the out-of-range value.
- Follow the out-of-range value to a satisfactory clinical resolution.

- Record as an AE any laboratory test value after start of study drug that:
 - The Investigator considers clinically significant.
 - Requires a subject to be discontinued from the study.
 - Requires a subject to receive treatment.

Blood will be obtained for CBC with differential as described in Section 12.1.10.

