Blinded adjudication of prohibited medication uses for rescue or for reasons unrelated to symptoms of CSU will be implemented before database lock.

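### Protocol 11.3, 12.1.10 and 20.9.1 give different end points for blinding differential counts, and 20.9.1 taken literally would release arm-revealing eosinophil counts of OLE entrants before blinded adjudication and lock

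*Protocol*

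**What the plan says.** Five places in the Protocol govern who sees differential counts, and when.

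- **11.3 Blinding.** Differential results, with eosinophils named, "will not be provided to the Investigator and Sponsor until after final database lock of the double-blind study to avoid bias". There is no OLE exception.
- **12.1.10, general rule.** Differentials are blinded from post-dose Day 1 "through Day 155 or ET and until database lock has occurred".
- **12.1.10, last sentence of the same paragraph.** For a subject who continues to the OLE, counts are blinded for the OLE Day 1 predose assessment and "will be unblinded after the subject has received the first dose of the study drug".
- **20.9.1 (Appendix 9).** "All differential blood counts will be blinded to the Sponsor and the site until after OLE Day 1 dosing".
- **4.4 and Table 1 note 14.** Post-treatment differentials collected in the double-blind period are withheld from sites and Sponsor. Neither place mentions release on entry to the OLE.

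On the work that needs a blind, SAP 4.2.5 says: "Blinded adjudication of prohibited medication uses for rescue or for reasons unrelated to symptoms of CSU will be implemented before database lock". SAP 5.6 makes decisions on protocol violations and population exclusions a precondition of lock.

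**The concern.** Eosinophil depletion is the drug's pharmacodynamic effect, and Protocol 12.1.10 itself recognises that the expected laboratory changes could bias blinded staff. That is why the counts go to a Safety Monitor.

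Two rules with different end points leave the central laboratory to choose one when it sets its release date. If it works from 20.9.1, which refers to *all* differential counts, an entrant's stored double-blind results would open once the first OLE dose is given. Sponsor and site could then infer the entrant's arm while decisions affecting that subject's data are still open. These are whether a medication use counts as an intercurrent event (which sets efficacy data to missing, or to non-response for binary endpoints), whether a deviation is major, and which population the subject belongs to. SAP 5.1 also allows alternative analysis methods to be considered up to lock.

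**Working it through.** The plan gives no figure on this point. The check compares the texts and works out the dates.

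**1. Do the end points differ?** Yes. 11.3 and the general rule of 12.1.10 end blinding at database lock (11.3 specifies the final double-blind lock). 20.9.1 and the last sentence of 12.1.10 end it after the first OLE dose. Neither OLE sentence says whether it opens results already stored or only samples drawn later.

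**2. Which samples are at issue?** Protocol 13.11 keeps a subject in the double-blind period until the first OLE dose. Everything from the Day 1 post-dose sample to the OLE Day 1 predose sample is therefore a double-blind sample. On a same-day OLE start, Table 10 note 16 has the CBC recorded only under Day 85, so the OLE predose count and the Day 85 double-blind count are one result.

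**3. Could these samples show the arm?** Protocol 2.3 reports for AK002-017 that "the PD effect (depletion of blood eosinophils) occurred within 1 hour of dosing". It lasted at least 1 month at 1 mg/kg and 3 months at higher doses. The intervals here are shorter:
- between doses: at most 21 days (10.1);
- last double-blind dose to Day 85: 11 to 17 days (10.1);
- last double-blind dose to OLE Day 1, allowing the 7-day delay: 11 to 17 + 7 = 24 days.

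All are under a month. A lirentelimab subject would be expected to remain depleted through the OLE Day 1 predose sample, and a placebo subject would not be depleted by drug.

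**4. And after the first OLE dose?** Every entrant has then received lirentelimab, with depletion expected within 1 hour. Both former arms should look alike, and these samples carry little information about the original assignment.

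**5. Is blinded work still open?** OLE Day 1 falls on nominal Day 85 to 85 + 7 = 92. Final lock waits for all subjects (Protocol 17.4). Take an entrant who enrolled on the same day as the last subject to stay out of the OLE and finish at Day 155:
- shortest lead: 155 − 92 = 63 days;
- longest lead: 155 − 85 = 70 days;
- at the extremes of the ±5-day windows: 150 − (90 + 7) = 53 to 160 − 80 = 80 days.

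Earlier enrollees have longer leads. Protocol 17.4 also has a provisional lock once all subjects complete Day 85, after which the code appears to become available to Sponsor analysts. Against that lock, an entrant who enrolled *d* days before the last subject has a nominal lead of *d* − 7 to *d* days. The documents do not give the length of enrolment, so *d* cannot be filled in.

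**6. Is the entrant's primary score exposed?** No. SAP 5.2 closes the Week 12 diary window no later than the OLE Day 1 dose.

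**The case against.** The strongest reply is that the texts agree when read together. 12.1.10 names the OLE Day 1 predose sample as one that is blinded, so its last sentence can be read by time of sampling: predose closed, later samples open. Section 4.4 and Table 1 note 14 go by period of collection, and 13.11 puts every pre-OLE sample in the double-blind period. The line in 20.9.1 is one bullet in a summary and does not expressly release stored results. This stands as the more coherent reading, and a reader who infers that the Protocol authorises release of double-blind counts goes too far. It does not remove the conflict: 20.9.1 covers all counts, 11.3 has no OLE exception, and nothing links them.

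The reply also says the impact is small. The censoring rules in SAP 4.2.5 are largely fixed, Appendix 1 works from ATC codes, mITT exclusions are tied to inclusion criteria 3 to 6, and the PP analysis is supportive. That is fair. Judgement remains in separating rescue from unrelated use, which is why the SAP wants that step blinded.

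Four stronger inferences are tempting but unsupported:
- **The counts show each entrant's arm.** The documents give no per-subject discrimination, and the depletion data in 2.3 come from healthy volunteers. Inference is plausible, not certain.
- **A head count.** With 10% dropout, 130 × 0.9 = 117 reach Day 85. An assumed uptake of 60% to 90% gives 117 × 0.60 ≈ 70 to 117 × 0.90 ≈ 105. The uptake is nowhere in the documents, and the count applies only on the literal reading.
- **Sites would learn what to look for in subjects still under double-blind treatment.** The Protocol already describes the depletion, and those subjects' differentials stay withheld.
- **A local-laboratory leak under 12.3.** The text reads "Clinical laboratory testing may be performed locally, if necessary, with prior approval from Allakos", so the Sponsor already controls this route, and 11.3 does not limit its rule to central results. Restricting these tests would also limit a means of following adverse events.

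**Conclusion.** The concern holds as an internal inconsistency with a possible unblinding route, not as a demonstrated unblinding. If stored double-blind counts are released, the arm of any OLE entrant could be inferred by Sponsor and site, nominally 63 to 70 days or more before the earliest final lock, given a non-OLE subject who enrolled no earlier. If only samples drawn after the first OLE dose are released, the exposure is near zero. The number affected depends on OLE uptake, which is not stated.

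What is at risk is the blinding of medication adjudication and of deviation and population decisions. The Week 12 diary scores themselves are not at risk. No size of bias can be derived from the documents. The conclusion assumes that depletion in this population resembles that reported in 2.3.

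**What to change.** In 20.9.1 and in the last sentence of the 12.1.10 paragraph, state that:
- only samples drawn after the first OLE injection are released to Sponsor and site;
- all differentials from the Day 1 post-dose sample through the Day 85 or OLE Day 1 predose sample stay blinded until final double-blind lock;
- the Safety Monitor keeps real-time access throughout.

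Add a cross-reference in 11.3 and set the central-laboratory release to match, keyed to collection time relative to the first OLE injection. No change to local or additional CBCs is needed.

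The cost is a few sentences and one laboratory setting. If the narrow reading was always intended, the edit only says so. The one drawback is that OLE sites would not see pre-OLE differentials before lock, but the Safety Monitor already reviews these and can escalate. Sample size and the analysis model are unaffected.
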